## 1. INTRODUCTION

### 1.1 SUMMARY

Russia and Eastern Europe continue to have one of the fastest growing HIV epidemics in the world, with highest transmission risks among people who inject drugs (PWID) and their sexual partners. While routine HIV testing within addiction treatment systems in Russia (i.e., narcology hospitals) is the norm, links between the narcology and HIV care systems are limited and ineffective. In St. Petersburg 50-60% of PWID are HIV-positive, yet among this population less than 10% are on antiretroviral therapy (ART). For Russia to make progress toward the UNAIDS 90-90-90 targets (i.e., 90% aware of HIV diagnosis, 90% of those diagnosed on ART and 90% of those on ART with suppressed HIV viral load [HVL]), a bold new strategy is required. The objective of this study, “Linking Infectious and Narcology Care – Part II (LINC-II),” is to implement and evaluate, via a two-armed randomized controlled trial among 240 HIV-positive PWID, a multi-faceted intervention combining pharmacological therapy (i.e., rapid access to ART and receipt of naltrexone for opioid use disorder) and 12 months of strengths-based case management. The central hypothesis is that LINC-II will lead to marked progress toward the achievement of the 90-90-90 HIV cascade of care targets among HIV-positive PWID, relative to current standard of care, and that LINC-II will facilitate health system coordination of narcology and HIV care. LINC-II aims to evaluate: 1) the effectiveness of LINC-II on undetectable HVL at 6 months and 12 months (primary outcome), initiation of ART within 28 days of randomization, change in CD4 count from baseline to 12 months, and retention in HIV care (i.e.,  $\geq 1$  visit to medical care in 2 consecutive 6 month periods); 2) the impact of LINC-II on coordinated care across the narcology and HIV health care systems, using mixed methods data from health care providers, administrators, and patients; and 3) the cost-effectiveness of the intervention to inform policy makers on scaling up the LINC-II approach both within Russia and other countries with HIV epidemics driven by injection drug use. The study’s goal is to improve upon current seek, test, treat, and retain efforts for HIV-positive Russian PWID in narcology care, a group routinely tested for HIV. If LINC-II is effective and can be embedded efficiently within the Russian and other medical systems challenged by HIV-positive PWID, then it has great potential to favorably impact the HIV epidemic in a key HIV population.

### 1.2 SIGNIFICANCE

The LINC-II study will assess the effectiveness and implications of an intervention designed to achieve 90-90-90 HIV care cascade targets by facilitating coordination of care between the addiction (i.e., narcology) and HIV treatment systems in Russia. Potential lessons learned in Russia should be applicable to all countries attempting to engage HIV-positive people who inject drugs in HIV care.

## 2. OVERVIEW OF STUDY DESIGN

### 2.1 STUDY AIMS

LINC-II's Specific Aims are the following:

**Aim 1:** *Evaluate the effectiveness of LINC-II on HIV care and health* compared to standard of care via a 2-armed RCT of 240 HIV-positive Russian PWID on the following outcomes:

- a. Primary: Undetectable HIV viral load at 12 months
- b. Secondary: Initiation of ART within 28 days of randomization;

Change in CD4 count from baseline to 12 months;

Retention in HIV care (i.e.,  $\geq 1$  visit to medical care in 2 consecutive 6 month periods)

Undetectable HIV viral load at 6 months.

HVL suppression and past 30-day opioid abstinence assessed at 6 and 12 months

**Aim 2:** *Evaluate the impact of LINC-II on coordinated care across the narcology and HIV health care systems* using mixed methods data from health care providers and administrators from both systems, as well as with LINC-II study participants (i.e., patients within these systems) to determine trends over time. Survey data and interviews will assess perceptions of whether the narcology and HIV care systems increased coordination of care over the period of the study, and qualitatively, how and why coordination does or does not occur, as well as the system implications of such coordination.

**Aim 3:** *Evaluate whether LINC-II is an affordable and cost-effective strategy* for achieving undetectable HVL in HIV-positive PWID. If the intervention is successful, it will be important to understand the net cost to be incurred by the health system and patients and LINC-II's cost-effectiveness compared to standard of care. This economic perspective will inform policy makers on scaling up the LINC-II approach both within Russia and other countries with HIV epidemics driven by injection drug use.

### 2.2 STUDY HYPOTHESIS

We hypothesize that participants randomized to the LINC-II intervention will have improved HIV care outcomes as compared to the control group, which will receive narcology hospital's standard of care.

### 2.3 STUDY OUTCOMES

[figure not shown]
**Aim 1.** The primary outcome for aim 1 is defined as an undetectable HVL at 12 months post randomization, assessed by study test within a window of 9–15 months. Secondary outcomes are initiation of ART within 28 days of randomization, change in CD4 count between baseline and 12 months (assessed by study test), retention in HIV care (at least 1 visit to medical care in 2 consecutive 6 month periods within 12 months of enrollment, assessed by medical record review and by self-report), undetectable HVL at 6 months post randomization assessed by study test, and a composite outcome for achieving both HVL suppression and past 30-day opioid abstinence assessed at 6 and 12 months.

## 2.4 STUDY DESIGN

LINC-II is a Randomized Controlled Trial (RCT) among 240 HIV+ PWID, which aims to test the LINC-II intervention, evaluate its impact on coordinated care and evaluate its cost-effectiveness. Eligible participants will be randomly assigned into one of two groups: 1) Control group receiving narcology hospital's standard of care or; 2) LINC-II intervention. The intervention for those randomized to the intervention arm starts in the narcology hospital: an HIV case manager (CM) will meet with the participant, participant will have accelerated access to ART medication with potential to initiate ART right at the narcology hospital, and the participant will receive a dose of injectable naltrexone (i.e., Vivitrol) for treatment of their opioid use disorder. Following discharge from the narcology hospital, participants will meet with the case manager over 12 months, receive implantable naltrexone (Prodetoxon) every 10-12 weeks (4 doses), and ideally start on ART at their first HIV care visit, if ART was not initiated at the narcology hospital. Study outcomes will be assessed at 6 and 12 months (Figure 1).

Figure 1 illustrates the design of this 2-arm RCT with 120 participants per arm.

**Figure: LINC-II Study Design**

Throughout the course of the study, participants will be expected to participate in three in-person assessments and blood draw visits (baseline, 24 weeks and 52 weeks). Intervention participants will receive 4 naltrexone implants while in the study. Ideally, implants will be inserted every 10-12 weeks starting at week 4 post-study enrollment (weeks 4, 16, 28, 40). Participants will be invited to come in every 4 weeks following implantation for medication visits. Ideally, medication visits will occur at weeks 4, 8, 12, 16, 20, 24, 28, 32, 36, 40, 44, 48, and 52. Full study assessments occur at weeks 24 and 52 (in addition to medication visit procedures). Implant visits 2, 3, and 4 will involve the collection of blood for laboratory testing to monitor liver toxicity.

## 2.5 STUDY SITE

St. Petersburg City Addiction Hospital (CAH) will be the site of participant recruitment. CAH is a government-funded 510-bed hospital, providing free addiction care to residents of the city of St. Petersburg, who are registered as having a substance use disorder (drug or alcohol). The hospital provides detoxification, early stabilization, and inpatient rehabilitation. The typical length of stay for hospitalized patients is one to two weeks.

St. Petersburg City AIDS Center will provide HIV care for the intervention group. A typical initial outpatient visit to initiate HIV care includes examination by an infectionist (physician), lab testing (e.g., HVL, CD4), and referrals (e.g., psychologist or addiction specialist). Some clinics have a narcologist on

staff to refer HIV-positive PWID to drug addiction clinics. HIV case managers, including some HIV-positive PWID in recovery (i.e., peers) have been introduced at the clinics. ART is available at no cost to all patients in Russia; however, only a small percentage of PWID actually receive this treatment.

Follow up study visits, naltrexone implants, and adverse event monitoring will occur at the Laboratory of Clinical Pharmacology of Addictions at the First St. Petersburg Pavlov State Medical University (PSMU) in St. Petersburg, Russia. PSMU is the major educational, scientific, and clinical medical institution for northwestern Russia.

Blood specimens for AST/ALT will be processed and analyzed at ImmunoBioService (IBS) under the direction of [name]. CD4 and HVL testing will take place at the City AIDS Center.

## **2.6 INCLUSION CRITERIA**

To be eligible to participate in the trial, participants will need to meet the following inclusion criteria:

1. 18 years or older
2. HIV-positive
3. Hospitalized at a narcology hospital
4. History of injection drug use
5. Current diagnosis of opioid use disorder
6. Provision of contact information for 2 contacts to assist with follow-up
7. Address within 100 kilometers of St. Petersburg
8. Possession of a telephone (home or cell)
9. Able and willing to comply with all study protocols and procedures

## **2.7 EXCLUSION CRITERIA AT STUDY ENTRY**

1. Not fluent in Russian
2. Cognitive impairment resulting in inability to provide informed consent based on research assessor (RA) assessment
3. Pregnancy, planning to become pregnant, or breastfeeding
4. ART use in past 30 days prior to hospitalization

5. Acute severe psychiatric illness (i.e. ,answered yes to any of the following: past three month active hallucinations; mental health symptoms prompting a visit to the ED or hospital; mental health medication changes due to worsening symptoms; presence of suicidal ideations)
6. Known history of liver failure
7. Known hypersensitivity to naltrexone
8. ALT or AST >5 times the upper limit of normal ((ALT > 225 for men and 170 for women; AST > 185 for men and women)
9. Known severe thrombocytopenia (<50K)
10. Known coagulation disorder/taking anticoagulation medications
11. Body habitus that precludes intramuscular injection (e.g., BMI < 17 or >45)
12. Known hypersensitivity to naloxone
13. Known history of Raynaud's disease
14. Known history of Itsenko-Cushing syndrome
15. Known history of generalized mycoses
16. Known history of glaucoma
17. Known history of osteoporosis.
18. Planned surgeries in the next 12 months

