### Medication Risks

The most serious risk of naltrexone (both implant and injection) is the potential for hepatocellular injury when taken in excessive doses (the margin of separation between the apparently safe dose of naltrexone and the dose causing hepatic injury may be only five-fold or less). Harm is less likely at the dosage provided in this study. In alcohol dependence trials, liver enzymes that are initially elevated (likely due to excessive alcohol use) decreased in participants taking naltrexone. As a precaution, participants will have ALT and AST repeated at implant visits 2,3, and 4, and if either liver enzyme is >5 times the upper limit of normal, results will be shared with participant during their suture removal visit and a repeat test will be done during their next medication visit. If any repeat test result is again >5 times the upper limit of normal, or if a patient is symptomatic (e.g. fatigue, anorexia, jaundice, nausea, vomiting, dark urine, light stool, abnormal pain), the patient will be referred to a hepatologist for further evaluation and a recommendation about continuing study medication. We expect this situation to be rare or non-existent based on prior experience with naltrexone. These precautions, combined with frequent contact with study staff, will provide thorough monitoring and appropriate response if evidence of liver damage emerges in the course of the study.

Normal ranges:

AST: Male: to 38 units/L; Female: to 32 units/L

ALT: Male: to 41 units/ L; Female: to 31 units/L

Exposure to naltrexone can precipitate severe withdrawal if the participant is physiologically dependent on opioids. To avoid unintended withdrawal, participants will be given a naloxone challenge prior to starting naltrexone, as described earlier.

Though data from the Lucey et al study (2008) using injectable naltrexone showed no effect of nonsteroidal anti-inflammatory drugs (NSAIDs) in patients taking naltrexone, other studies have shown that non-steroidals taken with naltrexone can increase the chances of liver damage. As a precaution, participants will be warned of this possibility and advised to take NSAIDs only if necessary, and to take low doses if use of these medications is necessary. Non-steroidal use will be recorded so that the potential for such interactions can be evaluated.

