### **3.6 SCHEDULE OF DATA COLLECTION**

Intervention Group								
		Pre-screen	Screener and Baseline	Implant visits	Medication Checks (every 4 weeks post implant)	6-month visit (24 weeks)	12 month visit (52 weeks)	

			Screener	Baseline			
Screening	Verification of HIV, pregnancy, AST/ALT	X					
	Screening Questions		X				
Enrollment	Sign Informed Consent		X				
	Complete contact information/verify numbers			X			
	Randomization			X			
Laboratory	Clinical Values			X	X	X	X
	Pregnancy Test		X		X	X	X
	Urine Drug Test			X	X	X	X
	CD4			X		X	X
	HVL			X		X	X
	ALT/AST				X		
Assessment	Full Study Assessment			X		X	X
	Qualitative Assessment			X		X	X
	Medical Record Review	X				X	X
Intervention	Symptom Management/Adverse Events			X	X	X	X
	Naloxone challenge			X	X		
	Naltrexone Injection			X			
	Naltrexone Implant				X		
	Brief Counseling				X	X	X
Other	Compensate for Participation			X	X	X	X
	Provide Resource Card			X			
	Report Adverse Events			X	X	X	X
	Complete Tracking Forms			X	X	X	X

Control Group						
		Pre-screen	Screener and Baseline Visit		6 mo (24 weeks)	12 mo (52 weeks)
			Screener	Baseline		
Screening	Verification of HIV, pregnancy, AST/ALT	X				
	Screening Questions		X			
Enrollment	Sign Informed Consent		X			
	Complete contact information/verify numbers			X		
	Randomization			X		
Laboratory	Clinical Values			X	X	X
	Pregnancy Test		X			
	Urine drug Test				X	X
	CD4			X	X	X
	HVL			X	X	X
Assessment	Full Study Assessment			X	X	X
	Qualitative Assessment			X	X	X
	Medical Record Review	X			X	X
Other	Provide Resource Card			X		
	Compensate for Participation			X	X	X
	Complete Tracking Forms			X	X	X

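### None of the liver-enzyme entry cut-offs equals five times the normal limits that the protocol prints, and no reason is given

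*Combined protocol and SAP*

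**What the plan says.** Two rules in the protocol rest on the same multiple of the upper limit of normal (ULN).

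- **Entry.** Section 2.7, item 8, excludes "ALT or AST >5 times the upper limit of normal ((ALT > 225 for men and 170 for women; AST > 185 for men". The sentence goes on to apply the AST figure to women too, so ALT has a cut-off for each sex and AST has one for both.
- **On study.** Section 3.3.C, Medication Risks, says that "participants will have ALT and AST repeated at implant visits 2,3, and 4". It then says that "if either liver enzyme is >5 times the upper limit of normal, results will be shared with participant", and a repeat test follows at the next medication visit. Referral to a hepatologist comes later: "If any repeat test result is again >5 times the upper limit of normal, or if a patient is symptomatic".

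The on-study rule has no absolute cut-offs. It is followed by normal ranges: "AST: Male: to 38 units/L; Female: to 32 units/L" and "ALT: Male: to 41 units/ L; Female: to 31 units/L". No other normal ranges for these enzymes appear in the document.

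On where the values come from, the Section 3.6 schedule lists "Verification of HIV, pregnancy, AST/ALT" in the pre-screen column, and Section 4.2 describes the pre-screen as a chart review. Section 3.7.B limits study AST/ALT testing to the intervention arm at implant visits 2, 3 and 4. Section 2.5 names one laboratory: "Blood specimens for AST/ALT will be processed and analyzed at ImmunoBioService (IBS"). It does not restrict that statement to follow-up samples.

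**The concern.** A cut-off described as a multiple of a normal limit should equal that multiple of a limit the protocol gives. Here none of the four sex-by-enzyme figures does. The structure differs too: AST has separate limits for men and women in Section 3.3.C and a single cut-off in Section 2.7.

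Item 8 can therefore give two answers for the same candidate, depending on whether the screener applies its words (with the printed ranges) or its numbers. The value also matters for safety. Section 3.3.C treats liver injury as the most serious risk of naltrexone. The entry value is the only scheduled liver-enzyme check before the injection and the first implant (ideally week 4). The first on-study test comes at implant visit 2 (ideally week 16).

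**Working it through.** **Inputs.** Entry cut-offs are from Section 2.7, item 8: ALT 225 (men) and 170 (women); AST 185 (both sexes). Printed ULNs are from Section 3.3.C, Medication Risks: ALT 41 (men) and 31 (women); AST 38 (men) and 32 (women), in units/L. Item 8 gives no units, so I assume the same ones.

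**Step 1: try to reproduce the entry cut-offs.** Multiply each printed ULN by 5 and compare.

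| | 5 × printed ULN | Entry cut-off | Difference | Relative difference | Cut-off ÷ ULN |
|---|---|---|---|---|---|
| ALT, men | 5 × 41 = 205 | 225 | +20 | 20/205 = +9.8% | 225/41 = 5.49 |
| ALT, women | 5 × 31 = 155 | 170 | +15 | 15/155 = +9.7% | 170/31 = 5.48 |
| AST, men | 5 × 38 = 190 | 185 | -5 | -5/190 = -2.6% | 185/38 = 4.87 |
| AST, women | 5 × 32 = 160 | 185 | +25 | 25/160 = +15.6% | 185/32 = 5.78 |

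None is reproduced. Swapping the sexes, swapping the enzymes or using one limit for both sexes does not help: the available products are 155, 160, 190 and 205, and none equals 170, 185 or 225. Rounding is not an explanation either, because the gaps run in both directions and reach 25 units.

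**Step 2: find the limits the cut-offs imply.** Divide each by 5: 225/5 = 45, 170/5 = 34, 185/5 = 37. These are whole numbers, which fits a correct calculation from some other reference set. None of them is printed in the document.

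**Step 3: find the values on which the two disagree.** Both rules use strictly greater than. For whole-number results on the printed ranges:

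- ALT 206 to 225 in men, ALT 156 to 170 in women and AST 161 to 185 in women: eligible by the numbers, yet above 5 × ULN.
- AST 186 to 190 in men: excluded by the numbers, yet not above 5 × ULN.

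For example, a woman with AST 170 (170/32 = 5.3 × ULN) passes entry, while the same value at implant visit 2 triggers result-sharing and a repeat test. A man with AST 188 (188/38 = 4.9 × ULN) is excluded.

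**The case against.** The best defence is that the two rules draw on different data. Entry values are read from hospital charts at pre-screen. Study samples are taken only at implant visits 2, 3 and 4, and the baseline blood draw in Section 4.4 lists only CD4 and viral load. The printed ranges directly follow the on-study rule, so they may be meant for study samples alone. The cut-offs are exact multiples of 45, 34 and 37, so the hospital laboratory may simply use those limits, with one AST limit for both sexes. If so, nothing was miscalculated and the discrepant bands disappear. Each rule can also be applied as written, at its own time, without anyone choosing between two figures.

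Much of this stands. A difference in reference ranges is a plausible explanation, and an arithmetic slip has not been shown. But the document does not state that explanation, print those limits or name their source. Section 2.5 names one AST/ALT laboratory without limiting its scope, and Section 3.3.C calls the on-study tests repeats, which links them to the entry value. Neither point proves that the printed ranges govern entry, but together they leave a reader with one laboratory, one set of ranges and figures that do not match. If two reference sets are in use, the remedy is still to say so.

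The objection that the consequences are limited is also fair: a first on-study value above the trigger leads only to sharing the result and a repeat test.

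**Conclusion.** The concern holds. On the only normal ranges in the document, the entry cut-offs are 4.87 to 5.78 times the ULN rather than 5, three too high and one too low for the stated multiple, and no reason is given.

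The size of the discrepancy depends on the printed ranges applying at entry. If the chart laboratory's limits are in fact 45, 34 and 37, only an unstated source remains. The document does not say how many candidates would fall in the discrepant bands.

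The effect is limited to eligibility within those bands and to how an entry value compares with the on-study trigger. Adverse-event recording of laboratory results in Section 6.2 depends on whether a finding is new, worse than baseline or clinically significant, not on this multiple. Power and the primary analysis are unaffected. It should still be corrected, because it is a safety-related eligibility threshold that does not match its own description.

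**What to change.** Reconcile Section 2.7, item 8, with the Medication Risks text in Section 3.3.C in one of two ways:

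1. make the numeric cut-offs agree with the stated multiple of the limits the protocol gives; or
2. state that different reference ranges apply to chart values at screening and to study samples, and give the limits and source of each, including whether AST limits differ by sex.

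Which figures are right is for the sponsor to decide. The cost is a one-line protocol clarification and, if the entry figures change, an update to the screening form.

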## 2.8 RECRUITMENT GOALS

We aim to randomize 240 participants over 30 months into the trial. Three to five days after City Addiction Hospital (CAH) admission and treatment for withdrawal symptoms, patients who have typical stays of 1 to 2 weeks will be recruited. This strategy will allow time to obtain HIV results (if not known), determine eligibility, obtain informed consent, perform baseline assessment, randomize, and, if applicable, schedule and conduct the 1st HIV case manager intervention session, conduct the naloxone challenge, and receive injectable naltrexone. This research study will focus on people who inject drugs (PWID), who comprise >90% of the CAH HIV-positive population.

In addition to the 240 RCT participants, we will also recruit up to 50 providers and administrators from HIV and narcology care systems to participate in a survey at study launch and up to 26 providers to participate in in-depth interviews at study launch and 12, and 24-months post-launch (plus short surveys) to explore their perspectives and experiences with care coordination between the narcology and HIV care systems.

A subset of LINC-II participants (at each time point n=10; 5 from intervention group, 5 from control group for a total n of up to 30 with 15 participants from each study arm) will also be invited to participate in in-depth interviews to discuss their experiences with care coordination at baseline, 6- and 12-months post enrollment.

